Describing Balance Function in Patients Post-COVID-19

NCT04914364

Document Date: July 30, 2021

Purpose of the Study

We hypothesize that patients with COVID-19 will have residual balance dysfunction that are more similar to those with neurological dysfunction than respiratory illness.

Background & Significance

People with cardiorespiratory dysfunction specifically chronic obstructive pulmonary disease (COPD) and lung transplantation have postural instability and increased risk of falls compared to age matched controls. People with COPD are 55% more likely to have falls than their non-COPD counterparts. It is speculated that this increase in fall risk is due to muscle weakness, attention and ability to dual task, decline in activity, polyneuropathy, and pain.

Ninety percent of patients with a history of COVID-19 report at least 1 neurological symptom. The neurological symptoms can occur before, during, or after the respiratory symptoms. Neurological symptoms include gustatory and olfactory dysfunction (35-88%), myalgia (19%), headache (15%), altered mental status, confusion or delirium (9%), and dizziness (9%). In an early report from Italy, they describe myopathy and neuropathy in addition to impaired balance and gait. Balance deficits could logically follow many of these neurological signs and symptoms. Although there is anecdotal evidence for imbalance immediately and long after COVID-19, we are unable to find a study that looked at balance quantitatively. Understanding balance dysfunction following COVID-19 can assist medical personnel in directing intervention for gait and balance dysfunction.

The act of maintaining upright posture or balance depends on both sensory and motor responses. Sensory information from vision, vestibular and somatosensory provide reference about where the body is in space and how it is moving so that appropriate motor responses can be generated. One can hypothesize that in patients with respiratory dysfunction, balance is affected through a lack of oxygen to the muscles making it a motor balance dysfunction. With neurologic dysfunction, difficulties can be seen with both the sensory and motor systems. Our balance outcome measures can differentiate between motor and sensory balance dysfunction. The Timed "Up & Go" is a measure of motor balance while the modified Clinical Test of Sensory Interaction measures the brain's use of visual, vestibular, and somatosensory for balance. We will describe the differences in the results of the TUG and the mCTSIB in patients with COVID-19 with previously documented balance dysfunction in patients with respiratory and neurological dysfunction (from existing literature).

Design & Procedures

Subjects who meet inclusion criteria (see below) will complete informed consent by the PI or one of the sub-investigators.

Subjects will complete the Activities-Specific Balance Confidence (ABC) Scale, provide number of falls in the past year and since hospital admission, and indicate their dizziness level on a 0-10 visual analog scale (VAS) for current, best and worst in the last 24 hours, and provide a description of dizziness (Asked "How would you describe your dizziness?").

HR, RR, BP, and SpO₂ will be measured at rest and after all outcome measures are completed. RPE (0-10 per modified Borg scale) will be measured after each outcome measure. In addition, HR will be measured after each outcome measure. SpO₂ will be continually monitored via pulse oximetry.

Fraction of inspired oxygen (FiO₂) will be titrated per MD orders. If SpO₂ drops below MD-specified parameters, patients will first be given a 3-minute seated rest break. If SpO₂ recovers above MD-specified parameters after rest break, activity will resume. If SpO₂ remains below MD-specified parameters after rest break or continues to drop with activity, FiO₂ will be titrated to maintain SpO₂ within MD-specified parameters.

The Timed “Up & Go” (TUG) and Modified Clinical Test of Sensory Interaction in Balance (mCTSIB) outcome measures will be randomized per Excel’s RAND function and performed in the order assigned.

During the TUG, subjects will be timed while standing from a standard chair, walking 3 meters at self-selected speed, turning around, walking back, and sitting back down. Subjects will be guarded by a physical therapist while they are walking to prevent falls.

During the mCTSIB, subjects will be timed (for a maximum of 30 seconds) standing on a firm surface, eyes open and eyes closed, then on a foam surface (Airex pad), eyes open and eyes closed. Subjects will have their arms folded across the chest and feet shoulder distance apart. If it is felt by the investigators that the subjects did not perform at their best level, they will be given a second trial. Subjects will be guarded by a physical therapist during balance activities to prevent falls.

Performance on the outcome measures will be recorded on a data sheet and entered into the spreadsheet manually.

Data will be recorded in a password-protected computerized database. Comorbidities and medications will be included from the medical record. Only Duke study personnel will access the medical record. The database will be de-identified before sharing with the co-investigators who are not Duke employees by a Duke employee.

This is a descriptive study and no intervention will be provided. All the examination/outcome measures are standard measures used in physical therapy.

Selection of Subjects

Inclusion Criteria:

- Age > 18 years and < 90 years
- Primary or secondary diagnosis of COVID- 19 during hospitalization and off COVID-19 isolation
- Receiving care in acute inpatient
- Ability to ambulate 20' with or without an assistive device without dropping >10% of resting SpO₂ (determined from existing PT evaluation)
- Ability to stand with no more than contact guard assistance (determined from existing PT evaluation)
- Not requiring use of mechanical ventilation
- Minimum resting SpO₂ of 88% with or without supplemental oxygen
- No neurological or orthopedic dysfunction that would affect balance
- Cognitively intact and able to follow directions and provide consent

Exclusion Criteria:

- History of 2 or more falls in the year prior to COVID-19 diagnosis or history of balance dysfunction

Subject Recruitment and Compensation

Potential participants will be identified by Duke study personnel using Maestro Care filters (i.e. COVID-19 and active physical therapy consults). Once identified, patients will be screened via chart review to ensure they meet inclusion and exclusion criteria for the study. The treating physical therapist or assigned nurse will approach all patients who meet the inclusion and exclusion criteria to see if they are interested in participating. Additional screening for current resting SpO₂ parameters and number of falls will occur upon approach as this information cannot be obtained via chart review. Consent will be obtained from either the PI or one of the sub-investigators. No compensation will be provided.

No sample size calculations were performed as this is a descriptive study. We plan to approach up to 40 subjects with a goal sample size of around 30-35 to describe balance in COVID-19.

Risk/Benefit Assessment

The study has small risk and no direct patient benefit but has the potential to provide information for patients who may benefit from future interventions aimed at addressing balance deficits in patients with COVID-19. Physical activity is generally considered to be safe for patients with cardiorespiratory conditions, but patients may incur the following risks:

- Risk of falls or musculoskeletal soreness or injury. This is not greater than what is experienced during standard physical therapy treatment. Subjects will be guarded to prevent falls.
- Risk of increased respiratory symptoms but these will be monitored and examination will be discontinued if subjects' SpO₂ drops > 10% of resting SpO₂. Any increased symptoms should be transitory.

Data Analysis & Statistical Considerations

This is a descriptive study so scores on the balance tests will be described by means and standard deviations for each group. Spearman correlation coefficients or linear regression will be used to determine if vital signs influence the balance scores.

Data & Safety Monitoring

The investigators will monitor for adverse events and report as required to the IRB. As there is no increase in risk beyond what is experienced in standard physical therapy intervention, no data monitoring committee will be used.

Duke study personnel who are interacting with patients will follow all Duke COVID-19 policies. Any required PPE will be worn during study visits. Inclusion criteria requires that patients be off isolation prior to approach for the study.

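### The plan compares TUG and mCTSIB scores only with diseased cohorts from the literature; with no normal or age-expected reference, it cannot show that the hypothesised balance dysfunction is present.

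*Combined protocol and SAP*

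**What the plan says.** The hypothesis in Purpose of the Study is that "patients with COVID-19 will have residual balance dysfunction that are more similar to those with neurological dysfunction than respiratory illness". It makes two statements: that dysfunction is present, and that its pattern is closer to neurological than to respiratory disease. The second presupposes the first.

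The planned comparison is at the end of Background & Significance. TUG and mCTSIB results will be compared descriptively "with previously documented balance dysfunction in patients with respiratory and neurological dysfunction (from existing literature".

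Under Data Analysis & Statistical Considerations, "scores on the balance tests will be described by means and standard deviations for each group". The groups are not defined. The only other analysis is that "Spearman correlation coefficients or linear regression will be used to determine if vital signs influence the balance scores".

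On size: "No sample size calculations were performed as this is a descriptive study", and "We plan to approach up to 40 subjects with a goal sample size of around 30-35 to describe balance in COVID-19". The age criterion is "Age > 18 years and < 90 years", with no age stratification or adjustment.

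**The concern.** Both literature populations are chosen because their balance is impaired. Comparison with them can show resemblance or difference, but it supplies no point that marks normal. The plan has no control group and no balance score from before the illness, so nothing inside the study fills that gap.

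The protocol's own background uses the missing standard: it describes instability in COPD and lung transplantation relative to age-matched controls. It also says that no quantitative study of balance after COVID-19 could be found, and that the results should help to direct treatment. Whether balance is abnormal, and in how many patients, is therefore the first thing a reader would want to know.

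Age adds a second difficulty. Over an eligible span of about seventy years, a pooled mean and SD cannot separate an older sample from an impaired one.

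**Working it through.** **1. Search for a reference.** The plan gives no figure to reproduce, so the main check is textual. These are all the places that could supply a standard of normal:

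- *Planned comparator (Background & Significance):* two diseased populations only.
- *Age-matched controls (Background & Significance):* mentioned for COPD and lung transplantation, not as a comparator for this study.
- *mCTSIB maximum of 30 seconds (Design & Procedures):* a timing cap, not called a norm or an impairment threshold. TUG has no counterpart.
- *Exclusion of earlier balance dysfunction or of 2 or more falls in the prior year (Selection of Subjects):* helps in reading a deficit as new, but does not show that one exists.
- *Balance confidence scale, falls and dizziness rating (Design & Procedures):* collected, with no analysis or cut-off stated.
- *Analysis section:* means, SDs and vital-sign associations; no cut-off, reference or confidence interval.

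None of these is a planned normal reference for TUG or mCTSIB.

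**2. Would a normative comparison be informative at the planned size?** Assumptions not in the documents: a reference value known without error, roughly normal scores, two-sided alpha 0.05.

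- 95% half-width of a mean, in SD units, is t(0.975, n−1)/√n. At n = 30: 2.045/5.477 = 0.37. At n = 35: 2.032/5.916 = 0.34.
- Shift detectable with 80% power, normal approximation (1.960 + 0.842)/√n: 0.51 SD at n = 30 and 0.47 SD at n = 35. The one-sample t calculation gives 0.53 and 0.49 SD.
- Proportion outside a limit, Wilson 95% interval: [p + z²/2n ± z√(p(1−p)/n + z²/4n²)]/(1 + z²/n), with z = 1.96 and n = 32. For 16/32 = 50%: 33.6% to 66.4%.
- If 5% of the reference population lies outside, 0.05 × 32 = 1.6 patients are expected. With 4/32 = 12.5% outside, the lower limit is 4.97%, just under 5%. With 5/32 = 15.6%, it is 6.9%. So 5 or more of 32 would put the whole interval above 5%.

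The comparison is therefore workable for a moderate or larger deficit.

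**3. Age mix, illustration only.** Assume that TUG lengthens by 0.5 to 1.5 s per decade, that the SD is 4 s, and that mean age is 70 rather than 50. None of these is in the documents. The age shift is 2 × 0.5 to 2 × 1.5 = 1 to 3 s. The 95% half-width at n = 32 is 2.040 × 4/√32 = 1.44 s, so the shift is 1/1.44 = 0.7 to 3/1.44 = 2.1 half-widths. This shows that age could matter on the scale of the sampling error. It does not estimate the bias in the planned comparison, which depends on the ages in the literature cohorts.

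**The case against.** The strongest reply is that the study calls itself descriptive and formally tests neither half of its hypothesis. That stands. A reader might infer that the first half alone was left untested while the second is tested; the documents do not support that contrast. The difference is narrower: the second half has a descriptive comparator and the first has none.

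A reader might also infer that patients with normal balance must come out as resembling one diseased cohort, because one will always be nearer. The plan sets no nearest-distance rule. It describes differences on two tests, read as motor against sensory balance. Patients with normal balance could be seen to score better than both cohorts, so a false conclusion is possible but not forced.

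The partial indicators also count for something. Failure to reach 30 seconds on the mCTSIB is visible without a norm, and falls, confidence and dizziness bear on the question. But the plan assigns none of them the role of showing impairment.

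Finally, norms are imperfect here. These are acute inpatients identified through active physical therapy consults, some with assistive devices or supplemental oxygen. Published procedures may not match the foam pad, arm and foot position, or discretionary second trial. This limits what a normative comparison can show, and it is more than a minor caveat. It restricts attribution to COVID-19; it does not remove the need for a reference before calling scores abnormal.

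**Conclusion.** The point holds as a gap between hypothesis and comparator. Followed exactly, the plan can describe similarity to impaired populations but has no reference by which to call TUG or mCTSIB scores abnormal. This rests on the text alone and needs no outside figure.

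The age-mix effect is a possibility of unknown size. A reader might take the 1 to 3 s illustration as a measured bias that would be mistaken for COVID-19 dysfunction. The documents do not support this: the slope, SD and mean ages are assumed, and the ages of the literature cohorts are not given.

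For a descriptive study of 30 to 35 patients this is a worthwhile, inexpensive improvement. It does not make the data unusable.

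**What to change.** Add to Data Analysis & Statistical Considerations, before any data are summarised:

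1. Name one published age-banded reference for TUG and one for the timed mCTSIB, with procedures as close to this protocol's as can be found, and list the differences.
2. Define outside the reference, for example beyond its 95% limit.
3. Report, as a descriptive supplement, the difference from age-expected values and the proportion outside with a 95% confidence interval. Read that proportion against the one expected in the reference population, for example 5%. Without a stated expected proportion, it tests nothing. Where mCTSIB times bunch at the 30-second cap, rely on proportions rather than means, and take the expected proportion from the source.
4. State that age is recorded in the dataset. It now appears only as an eligibility criterion.
5. Make the respiratory and neurological comparison after this step, giving the mean age of each literature cohort where reported.

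The cost is a short literature step and a few sentences of analysis text, with no new patients, visits or tests. The documents cannot confirm that well-matched norms exist for the whole age range. Because norms come from people who were not hospitalised, the result should be worded as below age-expected and not as caused by COVID-19.

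### SpO₂ is scheduled as data only at rest and at the close of testing, so the vital-sign analysis has no SpO₂ value matched to each balance test

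*Combined protocol and SAP*

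**What the plan says.** Design & Procedures gives SpO₂ two scheduled readings: "HR, RR, BP, and SpO₂ will be measured at rest and after all outcome measures are completed". Perceived exertion is taken after each test, and so is heart rate: "In addition, HR will be measured after each outcome measure". For SpO₂ during testing the text says only that "SpO₂ will be continually monitored via pulse oximetry".

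Two actions can intervene between the scheduled readings. "If SpO₂ drops below MD-specified parameters, patients will first be given a 3-minute seated rest break". If that does not suffice, "FiO₂ will be titrated to maintain SpO₂ within MD-specified parameters". Risk/Benefit Assessment adds that "examination will be discontinued if subjects' SpO₂ drops > 10% of resting SpO₂". The order of the TUG and the mCTSIB is randomized.

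Background & Significance suggests that in respiratory disease "balance is affected through a lack of oxygen to the muscles making it a motor balance dysfunction". Data Analysis & Statistical Considerations then states: "Spearman correlation coefficients or linear regression will be used to determine if vital signs influence the balance scores". It names no particular vital sign, no time point, and no choice between level and change. The only items Design & Procedures explicitly places on the data sheet are the test results.

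**The concern.** The drop in SpO₂ during a test is seen by staff and triggers rest, oxygen adjustment or stopping, yet nothing provides for writing it down. What is scheduled is a value before the tests and a value after them. In a subject who fell below the physician's limits, that later value may already reflect recovery.

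The planned analysis asks whether vital signs influence balance scores. SpO₂ is the vital sign closest to the respiratory mechanism the protocol proposes, so it deserves a measurement tied to the test being explained. Without one, a relation between desaturation and performance may look weaker than it is. Rest breaks and FiO₂ changes, which may themselves affect performance, would also leave no planned trace. Values not written down at the bedside may be unrecoverable later.

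**Working it through.** The plan states no power, alpha or target correlation, so there is no figure of its own to reproduce. The main check compares passages; the arithmetic after it is illustrative.

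**1. What is scheduled, and when** (Design & Procedures)

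| Variable | At rest | After each test | At close |
|---|---|---|---|
| Heart rate | yes | yes | yes |
| Perceived exertion | not stated | yes | not stated separately |
| SpO₂ | yes | no (monitored only) | yes |

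**2. What the closing SpO₂ represents**
- *Subject below the physician's limits during a test:* the closing value comes after rest and possibly after FiO₂ titration. Hypothetical case: rest 94%, low of 85% in the TUG, 93% at close. The in-test drop is 94 − 85 = 9 points, or 9/94 = 9.6% of resting. The scheduled readings show 94 − 93 = 1 point.
- *Subject who stays within limits:* no intervention is called for, but the closing value still follows only the test that came last. If the TUG came first, the mCTSIB lies between it and the closing reading: four stands of up to 30 seconds (4 × 30 = 120 seconds of timed standing), possibly with second trials. No scheduled SpO₂ reading then belongs to the TUG.
- *Subject whose examination is discontinued:* the closing reading is timed to completion of all tests, which does not occur, so it is undefined.

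**3. How far eligibility limits the problem** (Selection of Subjects)
- Subjects must have walked 20 feet without losing more than 10% of resting SpO₂. The TUG walk is 2 × 3 m = 6 m, and 6/0.3048 = 19.7 feet, so large drops over about that distance are largely screened out.
- Drops up to the limit remain possible. Read as a relative drop, 10% of a resting 94% is 9.4 points.
- The criterion comes from an existing physical therapy evaluation, not from the study session.

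**4. Illustration of what a poorly matched SpO₂ value could do**

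Input from the plan: a goal of about 30–35 subjects (Subject Recruitment and Compensation). Assumptions, none from the documents: true correlation ρ = 0.5 between in-test drop and balance score; two-sided alpha 0.05; correlation k between the recorded SpO₂ value and the true in-test drop; recorded value related to the score only through that drop, so the observed correlation is r = 0.5k.

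Fisher z with the Spearman variance 1.06/(n − 3): power = Φ(atanh(r) × √((n − 3)/1.06) − 1.96).

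Worked case, n = 30, k = 0.5: r = 0.25, atanh(0.25) = 0.255, √(27/1.06) = 5.05, and Φ(1.29 − 1.96) = 25%.

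| k | r | Power, n = 30 | Power, n = 35 |
|---|---|---|---|
| 1.0 | 0.50 | 79% | 86% |
| 0.8 | 0.40 | 57% | 64% |
| 0.5 | 0.25 | 25% | 29% |
| 0.2 | 0.10 | 7% | 8% |

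The loss ranges from moderate to almost total depending on k, which the documents do not give.

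**The case against.** The strongest reply is that the plan is silent rather than wrong. A reader might infer that in-test SpO₂ can never enter the analysis. The documents do not support that: the analysis sentence names no variable or time point, the oximeter runs throughout, and nothing excludes using its values. What stands is narrower: the plan does not provide for recording or analysing them, and following its schedule literally does not produce them.

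A reader might also infer that a null SpO₂ result would be taken as support for a neurological pattern. The protocol does not say so. It addresses that question by describing TUG and mCTSIB results against published respiratory and neurological findings; SpO₂ bears only on the separate vital-sign analysis.

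The proposed respiratory mechanism carries no timing, so resting SpO₂ is a legitimate variable and should stay. Rest and titration begin only below the physician's limits and aim for those limits, so not every closing value is altered. The eligibility walk narrows the range of drops further. These points reduce the effect without removing it.

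The illustration can fairly be attacked too. The correlations are assumed, no significance test is specified, and multiplying by k is doubtful when the distortion falls mainly on subjects who desaturated. It is not an estimate for this study.

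**Conclusion.** The point holds as a gap in measurement affecting a secondary analysis. SpO₂ has two scheduled readings. The second may be a recovered value, is not matched to a particular test, and is undefined after discontinuation. No recording of the in-test low, rest breaks, FiO₂ changes or early stops is planned. The association between desaturation during testing and balance scores may be weakened as a result.

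Its size cannot be derived from the documents. A reader might conclude that a real link would usually be missed, but that depends wholly on the assumed k: at k = 0.8 the illustrative power is still above one half. Nor would counting drops above 10% verify the statement that risk does not exceed standard physical therapy. The study has no standard-therapy comparison group, and the protocol treats that statement as a premise. The count is useful as description only.

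The change is worth making because it is nearly free and the stated schedule gives a poorer SpO₂ measure than the equipment already in use allows.

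**What to change.** Change the data collection and analysis text only; clinical management stays as it is.

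- On the existing data sheet, when heart rate and exertion are recorded for each test, also enter the lowest SpO₂ reached, any rest break, any FiO₂ change and any early stop.
- Define the closing vital signs as those taken when testing ends for any reason, including discontinuation.
- In the vital-sign analysis, include the test-specific SpO₂ (lowest value or drop from rest) alongside resting SpO₂. Note or adjust for supplemental oxygen and FiO₂ changes, since these also affect the in-test value.
- Report descriptively how many subjects had a drop above 10%.

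For that count, the 10% wording can be read as relative or as percentage points: from a resting 88%, a threshold of 88 × 0.9 = 79.2% or 88 − 10 = 78%. The text also does not connect the rest-and-titrate steps in Design & Procedures to the discontinuation rule in Risk/Benefit Assessment. These passages must be reconciled by the investigators.

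Cost: a few extra entries per test. The oximeter and the data sheet are already in place, and no added procedure is needed.

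### Patients admitted mainly for another acute illness can be counted in the COVID-19 balance means, and no planned data item or analysis would identify them

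*Combined protocol and SAP*

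**What the plan says.** - **Who is eligible.** Selection of Subjects (Inclusion Criteria) requires a "Primary or secondary diagnosis of COVID- 19 during hospitalization and off COVID-19 isolation". No section restricts the reason for admission.
- **Screens for other causes of imbalance.** The same list requires "No neurological or orthopedic dysfunction that would affect balance". The Exclusion Criteria remove patients with a "History of 2 or more falls in the year prior to COVID-19 diagnosis or history of balance dysfunction". The other criteria (walking and standing ability, SpO₂, ventilation, cognition) limit how impaired a participant can be, not why.
- **How cases are found.** Subject Recruitment and Compensation describes a chart filter on COVID-19 and an active physical therapy consult. Whatever illness prompted the consult, the patient passes the filter.
- **What is taken from the chart.** Design & Procedures: "Comorbidities and medications will be included from the medical record". Primary or secondary status and admitting reason are not named.
- **Analysis.** Data Analysis & Statistical Considerations says that "scores on the balance tests will be described by means and standard deviations for each group". No group is defined anywhere. The only influences examined are vital signs: "Spearman correlation coefficients or linear regression will be used to determine if vital signs influence the balance scores".
- **Comparator.** Background & Significance sets the results against published values for respiratory and neurological patients. There is no concurrent group of inpatients without COVID-19.

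**The concern.** The hypothesis in Purpose of the Study is about attribution: the balance deficit is taken to belong to COVID-19 and is classed as closer to a neurological or to a respiratory pattern. A patient in hospital mainly for a different acute illness, with COVID-19 coded second, contributes a TUG time and mCTSIB times that partly reflect that other illness. Without a field that marks such patients, neither the investigators nor a reader can tell how much of the mean they account for.

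The mixing can fall on the axis that the study wants to judge. Background & Significance treats TUG as the motor measure and suggests that respiratory dysfunction acts through motor balance. Because neurological dysfunction affecting balance is screened out, the other illnesses that remain may act mainly on motor performance. That could slow TUG and move the profile towards the respiratory pattern. This direction is a possibility under the protocol's own reasoning; the documents do not establish it.

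**Working it through.** **Plan's own figure.** The goal of about 30–35 subjects is given without a calculation, so there is nothing to reproduce. It is used below only as n.

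**Inputs**

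| Input | Value | Source |
|---|---|---|
| n | 30 and 35 | Subject Recruitment and Compensation |
| f, share admitted mainly for another acute illness | 10–50% | Assumption; not in the documents |
| d, difference in mean score for those patients, in within-type SD units | 0.3–1.0 | Assumption; not in the documents |

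**Shift in the pooled mean.** Shift = f × d. The pooled SD is √(1 + f(1 − f)d²), and the standard error (SE) is pooled SD/√n.

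| f | d (SD) | Shift (SD) | Shift/SE, n = 30 | Shift/SE, n = 35 |
|---|---|---|---|---|
| 10% | 0.3 | 0.03 | 0.16 | 0.18 |
| 10% | 1.0 | 0.10 | 0.52 | 0.57 |
| 30% | 0.5 | 0.15 | 0.80 | 0.86 |
| 30% | 1.0 | 0.30 | 1.49 | 1.61 |
| 50% | 0.5 | 0.25 | 1.33 | 1.43 |
| 50% | 1.0 | 0.50 | 2.45 | 2.65 |

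Worked row: f = 0.30 and d = 0.5 give a shift of 0.15. The pooled SD is √(1 + 0.3 × 0.7 × 0.25) = 1.026, so shift/SE = 0.15 × √30/1.026 = 0.80.

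For scale, the 95% half-width of a mean is 1.96/√n, which is 0.36 SD at n = 30 and 0.33 SD at n = 35. The shift therefore runs from negligible to larger than that half-width.

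**What a split would cost in precision.** This uses the same formula with the smaller n.
- From 30 subjects, 27 (f = 10%) down to 15 (f = 50%) would remain, with half-widths of 0.38 to 0.51 SD.
- From 35 subjects, 31 down to 17 would remain, with half-widths of 0.35 to 0.48 SD.
- If n falls from 32 to 22, the SE rises by a factor of √(32/22) = 1.21, about 20%.
- For the difference between two subsets of sizes a and b, the half-width is 1.96 × √(1/a + 1/b). Over these cases it runs from about 0.66 SD (18 and 17) to 1.19 SD (3 and 27). A formal comparison of the two would be uninformative.

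**The case against.** **Secondary does not mean unrelated.** The primary diagnosis may be a complication of COVID-19, and such a patient belongs in the target population. This stands. It is why the admitting reason is needed as well as the coding status, and why a comparison restricted to primary diagnoses is a poor choice for the main result: a coding label could drop relevant patients, at a cost in precision.

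**The other criteria limit severity.** Participants must walk 20 feet without a large fall in SpO₂, stand with at most contact guard assistance, be off mechanical ventilation and be cognitively intact. This makes a very large difference less plausible. It does not remove cardiac, other pulmonary, infectious or abdominal admissions.

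**Comorbidities and medications are collected.** Some description of other illness is therefore possible. The point stands only in part, because the admitting reason is not named as an item and no planned analysis uses the comorbidity data.

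**The study calls itself descriptive and small, and it lacks concurrent controls.** The missing control group is the larger limit on attribution, and this change leaves it in place. But the description is then set against disease-specific literature, so who is being described still matters.

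**Pooling is inferred.** The plan speaks of scores "described by means and standard deviations for each group", which could mean that a split was intended. With one cohort and no definition, a reader cannot tell.

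**Conclusion.** The concern holds as a gap in identification. Imbalance from a non-neurological, non-orthopedic admitting illness can be counted in the COVID-19 means, and nothing planned would show whether it was. The absence of a limit on admitting illness, of a named data item and of a planned separation rests on the text. The size rests entirely on the assumed shares and differences: about 0.03–0.50 SD, or roughly 0.2 to 2.7 SE at n = 30–35. The documents give nothing that places the study within that range.

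A reader might infer that every patient with a secondary diagnosis was admitted for something else, so that unrelated imbalance is in fact being counted as COVID-19 imbalance. The documents do not support this. They do not say what the primary diagnoses would be, how many patients would have COVID-19 coded second, or how their balance would differ. Nor do they support making the primary-diagnosis patients the main comparison. Admitting both types is an explicit eligibility choice, and the undefined word for groups cannot be read as meaning these two strata.

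This is a cheap improvement that lets the study check its own attribution. It is not a defect that invalidates the description.

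**What to change.** Keep eligibility unchanged and the full sample as the main description. Then:

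1. In Design & Procedures, add to the chart items whether COVID-19 was the primary or a secondary diagnosis, and the reason for admission.
2. In Data Analysis & Statistical Considerations, state what a group is, and report the TUG and mCTSIB mean and SD by diagnosis status alongside the full sample.
3. Repeat the literature comparison as a sensitivity description without patients whose admission was unrelated to COVID-19. Patients admitted for a COVID-19 complication stay in, however COVID-19 was coded.

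The cost is a small addition to an abstraction from a chart already reviewed for eligibility, and a few extra table rows. Study procedures and patient burden do not change. The downside is a smaller, less precise subset: going from 32 to 22 subjects raises the SE by about 20%. The split should be presented as descriptive only, with no test between the subsets.
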